8.1.6 Prior and Concomitant Medications

Prior and concomitant medications will be captured separately for BCC (facial) and other indications.

All medications ongoing in the 12 months prior to Baseline or ongoing at any time during the study will be recorded in the eCRF. The start date for all medications that were started during the study period must be reported. Likewise, the end date for all medications that were discontinued during the study period must be captured.

8.1.7 IP Application

For the first application, the subject will apply the IP at the study site under the direction of the Study Coordinator (or designee). The IP should be applied after all clinical assessments. Additional information on IP application is available in Section 10.4.

8.1.8 Compliance

Patients will be dispensed a diary to maintain a log of their IP application.

8.1.9 Unscheduled Visit

Subjects may return to the site for unscheduled visits in the event of an AE, SAE or as deemed necessary by the Investigator. The same procedures as described in the post-Baseline Visits may be conducted. For other subject care management, the Investigator may refer the subject to their primary care physician and/or their PSCP. Data collected will be reported in the 'Unscheduled Visit' eCRF page.

8.2 Efficacy Assessments

At the Baseline visit, the number of lesions on the face that are suspicious for BCC will be recorded. Additionally, the number of lesions on the face that are suspicious for BCC and that the patient consents to have removed in accordance with PI recommendation will also be recorded. These will be removed prior to the next Post-baseline quarterly visit.

At all quarterly visits, the number of lesions on the face that are suspicious for BCC will be recorded. Additionally, the number of lesions on the face that were suspicious for BCC and removed since the last visit will be recorded. Finally the number of lesions on the face that were suspicious for BCC, removed and confirmed on histology to be BCC will be recorded.

The count of facial lesions will exclude lesions on the face where IP should not be applied (i.e eyelids). Face is defined as in Section 10.4.

8.2.1 Biopsy

This is a mandated study procedure for all lesions suspicious for BCCs that were removed (irrespective of the treatment modality). All biopsies need to be reviewed and reported by a licensed physician with appropriate experience. The biopsy diagnosis will be captured in the eCRF. The detailed report of the biopsy will be part of the source document.

8.2.2 Surgery

During the study, only lesions that the patient consents to have removed in accordance with the PI recommendation will be removed.

Per local standard of care, the PI may decide to biopsy the lesion first and remove it based on histopahtologiuc confirmation. Alternately, this may be a one step procedure where the lesion is removed and biopsied at the same time.

- f Physical examinations will include collection of vital signs and weight (and height at Baseline only). Additional PEs may be collected according to any signs/symptoms and/or positive findings at previous PE.
- Serum pregnancy test at Screening and End of treatment/Exit Visit. For Study 301 subjects a negative serum pregnancy test result from Study 301 is acceptable if the test was done within 7 days of the Screening Visit of this study. Urine pregnancy test at all other visits.
- h Efficacy assessments include number of lesions removed by surgery since last assessment and count of BCCs. Lesions may be removed at any time per PI convenience but before the subsequent visit. Lesions identified at the End of treatment/Exit Visit, must be removed within 15 days of this visit.
- ⁱ AEs that occurred after signing of the informed consent will be recorded.
- J Subjects will be trained on how to appropriately apply IP and comply with study procedures. Additional reminders may be provided at subsequent visits, as appropriate.
- k IP is administered after all other assessments are completed and is followed by a 30-minute observation period.
- All IP tubes (used, partially used, and/or unused) will be returned and weighed. The weight will be recorded on the appropriate eCRF.

8.3 Safety Assessments

The safety assessments in the study include vital signs, AEs and dermal safety assessments (Section 11.1)

8.3.1 Dermal Safety and Tolerability Events

Safety and tolerability will be evaluated through assessment of selected local signs and symptoms (pain/burning, pruritus, erythema, edema, and crusting) on the face. These assessments will be performed prior to the application of IP. Any local skin reaction that requires use of a concomitant therapy or causes interruption or discontinuation of the IP should be reported as a safety event. These events will be assessed for severity, relative to the skin reactions scale (Table 2).

Table 2: Dermal Safety and Tolerability Scales

Score	Grade	Description				
Pain/Burning: as reported by the subject as being the greatest intensity they have experienced						
on the face within the last 24 hours at enrollment or since the last visit at subsequent visits.						
0	None	No pain/burning				
1	Mild	Slight burning/stinging sensation; not really bothersome				
2	Moderate	Definite warm, burning/stinging that is somewhat bothersome				
3	Severe	Hot burning/stinging sensation that causes definite discomfort and may interrupt daily activities and/or sleep				
Pruritus	s: as reporte	d by the subject as being the greatest intensity they have experienced on				
the face	within the la	ast 24 hours at enrollment* or since the last visit at subsequent visits.				
0	None	No pruritus				
1	Mild	Slight pruritus, not really bothersome				
2	Moderate	Definite pruritus that is somewhat bothersome				
3	Severe	Intense pruritus that may interrupt daily activities and/or sleep				
Erythema: facial erythema as assessed by the Investigator						
0	None	No erythema present				
1	Mild	Slight pink coloration				
2	Moderate	Definite redness				
3	Severe	Marked erythema, bright red to dusky dark red in color				
Edema:	facial edem	a as assessed by the Investigator				
0	None	No edema				
1	Mild	Slight, but definite edema				
2	Moderate	Definite edema				
3	Severe	Marked edema				
Crusting: facial crusting as assessed by the Investigator						
0	None	No crusting				
1	Mild	Slight, but definite crusting				
2	Moderate	Definite crusting				
3	Severe	Marked crusting				

^{*}Enrollment in this table refers to both Screening and Baseline Visits

8.3.2 Physical Examination and Vital Signs

Physical examinations (PEs) including vital signs (blood pressure, heart rate, respiration rate, and temperature), weight will be collected and reported. Height will be collected at the Baseline Visit only. Clinically significant changes from Baseline will be captured as AEs. Changes in BCC count will be captured separately as efficacy assessments and not as a PE assessment. Changes in BCC count or size will not constitute AEs.

8.3.3 Pregnancy Tests

All WOCBP will have a pregnancy test done at all visits, as per the SoA (Table 1). If the WOCBP becomes pregnant during the course of the study, she must immediately stop applying the IP and report the finding to the Investigator. Potential teratogenicity should be discussed at each visit with WOCBP and with male subjects with partners who are WOCBP.

9 TREATMENT PLAN

9.1 Methods of Assigning Subjects to Treatment Groups

This is an open label study where all patients will receive Patidegib Topical Gel 2%.

9.2 Treatment Compliance

Subjects will be required to return the IP tubes that are used and/or unused. Each subject will be instructed on the importance of both the application of the IP and return of the used and unused IP tubes. Each tube will be weighed when returned and the results will be entered on the source document and eCRF.

Patients will be dispensed a diary to maintain a log of their IP application. Any interruptions in the schedule of IP administration or use of prohibited concomitant medication will be recorded in the eCRFs.

9.3 Protocol Deviations

A PD is any change, divergence, or departure from the study design or procedures defined in the protocol. Major PDs are a subset of PDs that might significantly affect the completeness, accuracy, and/or reliability of the study data or that might significantly affect a subject's rights, safety, or well-being (FDA sheets and notices). If a major (important) PD has been identified, it should be communicated to and discussed with the Medical Monitor. A corrective and preventative action (CAPA) plan may be required to be instituted in the case of major PDs at the site. In the event of recurring major PDs, the site enrollment may be halted by the Medical Monitor, in consultation with PellePharm, until a CAPA plan has been instituted and the issue(s) resolved. PDs should be reported on at least an annual basis to the Central IRB or the site's local IRB.

For IP received undamaged, IP will be inventoried and the IP inventory/accountability log completed.

The subject will return all IP gel tubes (used, partially used, and/or unused) at their subsequent study visit. If any IP gel tubes are lost or damaged between clinic visits, additional IP may be provided to the subject. The goal is to ensure that the subject has an adequate supply of IP to be able to administer all scheduled treatments.

Refer to the Pharmacy Manual for additional details about administration requirements, IP supply, and accountability procedures.

10.3 Storage and Handling of Investigational Product

The IP tubes should be stored under controlled room temperature at 20-25 °C (68-77 °F) with excursions allowed from 15-30 °C.

10.4 Application

The IP should be applied to the face, which will be defined as the area extending from the anterior hairline to the jaw line (except the eyelids) including the ears. If the anterior hairline is receding, application of IP to the forehead will extend no more than 9 cm above the eyebrow or superior orbital ridge.

The initial application of the IP will take place in the clinic under observation. The Investigator or site personnel will instruct the subject on how to apply the IP at the Baseline Visit and the subject will apply the IP at that visit under observation. The Investigator or site personnel will instruct the subject on the proper use of laminated dosing cards during the Baseline Visit. Subjects will apply to the face an amount squeezed out as a specified amount on the laminated dosing card avoiding the eyelids (as described above and in the Pharmacy Manual). If no observable AEs are noted within a observation period after their first application, subjects can leave the site. No other IP applications at subsequent visits will be required to be observed in the clinic setting.

In addition to the verbal instructions given during the visit, written and/or other media IP application instructions may be provided to the subjects. Subjects should be encouraged to keep facial hair short enough to allow adequate application of IP to the face, and subjects must remove make-up prior to IP application. Make-up should not be applied any sooner than 30 minutes after the application of IP. If feasible the application of make-up may be deferred for as long as possible. Subjects will be instructed to wash their face and hands within approximately 10 minutes prior to IP application. Subjects will be advised to minimize exposure to direct sunlight and to wash their hands before and after application of the IP.

If an IP application has been missed or delayed such that there would be between applications, the subject should not apply that dose of IP and just wait to apply the next

dose. The importance of IP compliance should be discussed with the subject during each site visit.

Subjects will be instructed to store their IP in a secure location away from children. WOCBP should not come in contact with the gel unless using contraception as specified in this protocol.

If it is suspected that inappropriate amounts of IP are being applied by the subject further review of IP application in the clinic may be warranted.

10.5 Investigational Product Accountability and Disposal

Upon receipt of the IP, the Investigator (or designee, e.g., study center pharmacist) will acknowledge receipt of the IP after reviewing the shipment's content and condition. The Investigator (or designee) is responsible for ensuring that the designated study site staff conduct a complete inventory of study materials and assume responsibility for their storage and dispensing. The Investigator (or designee) must agree to keep all study materials in a secure location with restricted access. The Investigator (or designee) will keep a record of the inventory and dispensing of all IPs. This record will be made available to the Study Monitor for the purpose of accounting for all clinical supplies. Any significant discrepancy and/or deficiency must be recorded with an explanation.

All supplies sent to the investigators will be accounted for and, in no case, used in any unauthorized situation. Each tube of IP administered at the study center will be administered by qualified study center staff. At each site visit, IP compliance will be discussed with the subject.

At the end of the study, following final IP inventory reconciliation by the monitor, the study site will dispose of and/or destroy all supplies (including used, partially used, and/or unused tubes of IP) where possible, in compliance with the site's SOPs for IP disposal/destruction. In the event that the site is unable to dispose of and/or destroy IP supplies, the Sponsor will be notified and a third-party vendor may be contracted to manage destruction of IP supplies.

Refer to the Pharmacy Manual for additional details about IP accountability procedures, including the IP accountability log.

11 SAFETY INSTRUCTIONS AND GUIDANCE

11.1 Adverse Events

11.1.1 Definition of Adverse Event

An AE is any untoward medical occurrence in a subject administered a medicinal product and which does not necessarily have a causal relationship with the medicinal (investigational) product. AEs include any unfavorable and unintended illness, sign, symptom, clinically significant laboratory test abnormality, or disease associated with the use of a medicinal (investigational) product that has appeared or worsened during the course of the clinical trial, regardless of causal relationship to the medicinal (investigational) product under study.

Subjects will be questioned about any concurrent illness or sign or symptom. Any incidence of these signs or symptoms will be reported on the AE eCRF.

Vital signs and laboratory abnormalities are to be recorded as AEs only if they are clinically significant (for example: are symptomatic, requiring corrective treatment, leading to discontinuation or fulfilling a seriousness criterion). A laboratory abnormality that is part of an efficacy endpoint (e.g., histologic confirmation of BCC on a biopsy) is not to be reported as an AE.

An unexpected AE is one that is not listed in the Investigator's Brochure (IB) or is not listed at the specificity or severity that has been observed.

11.1.2 Documenting Adverse Events

It is the responsibility of the Investigator to document in the eCRF all AEs/SAEs that occur during the course of the study. AEs/SAEs should be collected after the informed consent form is signed and usually at the Screening visit. The AEs/SAEs should be documented as a single medical diagnosis. When this is not possible, the AE/SAEs should be documented in terms of signs and/or symptoms observed by the Investigator or reported by the subject at each study visit.

All AEs/SAEs occurring after the subject signs the informed consent through the last study visit must be reported, regardless of whether or not the AEs/SAEs are considered drug-related. All AEs/SAEs, whether in response to a query, observed by the study site personnel, or reported spontaneously by the subject, will be recorded.

At each visit during the study, the subject will be assessed for the occurrence of new and ongoing AEs. Dermal safety and tolerability assessments that result in the subject requiring a concomitant therapy or discontinuation from the study will be reported as an AE/SAE. The following data will be collected on all AEs and recorded on the appropriate eCRF:

- Event name (diagnosis preferred, if unknown, record the signs/symptoms)
- Onset date and end date

- Maximum severity
- Seriousness
- Action taken regarding IP
- Corrective treatment, if given
- Outcome

In addition, the Investigator's assessment of causality will be recorded.

It is not necessary to capture multiple occurrences of an AE separately if the event recurs at short intervals. In such instances the end date of the AE is the date when the event resolved last and did not recur. If however the event recurs after long intervals, then the subsequent event may be captured as a separate event. The PI may use his/her discretion to determine what constitutes a long or short interval between events and which event is reported once versus more than once. Protocol defined endpoints (e.g new BCCs on the face, nSEBs on the face and BCC surgeries on the face) will be summarized as efficacy parameters and are not to be reported as AEs/SAEs.

In the clinical database, information pertaining to all AEs including SAEs are to be recorded for a minimum up to the 30 day follow up visit. In the source documents, any and all AEs including SAEs must be thoroughly documented to conclusion or in the opinion of the investigator, the event has resolved or stabilized.

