11. The subject is willing to forego treatment of facial BCCs with anything other than the study IP except when the Investigator believes that delay of treatment of a BCC potentially might compromise the health of the subject. In such instances, the only other allowed form of treatment is surgical.

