11.1.3 Serious Adverse Events

All AEs will be assessed as either serious or non-serious.

An SAE or serious adverse reaction is defined as any untoward medical occurrence that at any dose:

- Results in death
- Is immediately life threatening, (the term "life threatening" in the definition of "serious" refers to an event in which the subject is at risk of death at the time of the event; it does not refer to an event which hypothetically might have caused death if it were more severe)
- Requires in-patient hospitalization or prolongation of existing hospitalization (hospitalization for elective surgery for a condition present at Screening is not considered an AE)
- Results in persistent or significant disability/incapacity (permanent or substantial disruption of a person's ability to conduct normal life functions)
- Is a congenital anomaly/birth defect
- Is a medically important event that may not be immediately life threatening or result in death or hospitalization, but may jeopardize the subject and may require medical or surgical intervention to prevent any of the above listed outcomes

If the BCC surgery requires, as per standard of care, that the patient be hospitalized, then this hospitalization is not an SAE.

Note: A spontaneous abortion will be considered an SAE and must be reported per Reporting of SAEs under Section 11.1.6. Pregnancy in and of itself is not an SAE, but a subject who becomes pregnant must discontinue IP application immediately and the pregnancy will be followed to term (and ideally the child will be followed afterward if the subject consents) or termination. Any birth defect or other serious issue that may arise during the pregnancy or due to fetal exposure will be considered an SAE.

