12.6 Assessment of Efficacy

12.6.1 Efficacy Endpoints

The efficacy endpoints are as follows:

- 1. The number of facial BCCs removed by surgery (per Investigator determination) and histologically verified as BCC; from Baseline to Month 12
- 2. The number of facial BCCs removed by surgery (per Investigator determination) and histologically verified as BCC; from Baseline to Month 6.
- 3. The number of facial BCCs removed by surgery (per Investigator determination) from Baseline to Month 12.
- 4. The number of facial BCCs removed by surgery (per Investigator determination) from Baseline to Month 6.
- 5. Change from Baseline to Month 12 in the total number of facial lesions suspicious for BCC
- 6. Count of facial lesions suspicious for BCC over time
- 7. aBCCdex change in lesion score from Baseline to Month 12

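### The AE/SAE exemption for facial BCCs has no seriousness limit, and two of its three example endpoints are not endpoints of this study

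*Protocol*

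**What the plan says.** Four protocol rules keep facial BCCs out of safety reporting.

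- **11.1.2** gives new facial BCCs as its first example of a protocol-defined endpoint, followed by "nSEBs on the face and BCC surgeries on the face) will be summarized as efficacy parameters and are not to be reported as AEs/SAEs".
- **8.3.2**: "Changes in BCC count or size will not constitute AEs".
- **11.1.1** treats histology that feeds an efficacy endpoint the same way: "e.g., histologic confirmation of BCC on a biopsy) is not to be reported as an AE".
- **11.1.3** removes one kind of hospital stay: "If the BCC surgery requires, as per standard of care, that the patient be hospitalized, then this hospitalization is not an SAE".

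Only the last is conditional, since it applies when admission is standard of care. The other three are not limited by severity or seriousness.

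On the efficacy side, Protocol 12.6.1 and SAP 6.2.2 carry the same seven endpoints. The first is "The number of facial BCCs removed by surgery (per Investigator determination) and histologically verified as BCC; from Baseline to Month 12", and the fifth is "Change from Baseline to Month 12 in the total number of facial lesions suspicious for BCC". SAP 6.2.3 adds seven exploratory endpoints, all patient-reported. Safety and tolerability is the primary objective (Protocol 5.1).

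**The concern.** Exempting an expected disease event from AE reporting is usually justified by its being analysed elsewhere. Here that justification is incomplete: two of the three named events are not analysed as such anywhere in the plan. The rule also names SAEs expressly, so it reaches events that would otherwise be notified to the sponsor within 24 hours under 11.1.6.

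The endpoints are counts and questionnaire scores. A facial BCC that grows, invades or leads to a serious outcome can be left out of the safety tables by rule while looking in efficacy like any other lesion. In an uncontrolled study whose primary objective is safety, a reader of the final report would want to know whether any facial BCC became serious on treatment. As written, the report may not be able to say.

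**Working it through.** The plan gives no figure on this point, so the check sets the texts side by side.

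**Step 1. Are the named endpoints endpoints?** Inputs: Protocol 12.6.1, SAP 6.2.2 and SAP 6.2.3.

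| Type of endpoint | Number |
|---|---|
| Facial BCCs removed by surgery (with or without histology; Month 6 or 12) | 4 |
| Facial lesions suspicious for BCC (change; count over time) | 2 |
| Patient-reported (aBCCdex lesion score, plus 7 exploratory) | 1 + 7 = 8 |
| Total | 4 + 2 + 8 = 14 |

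Against the examples in 11.1.2:

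- BCC surgeries: 4 of 14.
- New facial BCCs: 0 of 14.
- Facial nSEBs: 0 of 14. The abbreviation list defines SEB but not nSEB, and nSEB appears only in 11.1.2.

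**Step 2. Can new lesions be recovered from the counts?** Let N0 and N12 be the suspicious-lesion counts at Baseline and Month 12, and R the number removed between them. Then N12 = N0 + new − R − resolved, so new − resolved = N12 − N0 + R. Protocol 8.2 records N0, N12 and R. It does not record lesions that resolve without removal, and describes no lesion-level tracking. New lesions therefore cannot be separated from resolved ones, and the suspicious-lesion counts are not histologically confirmed.

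**Step 3. Is severity of a lesion recorded?** Protocol 8.2 and the efficacy footnote to Table 1 describe counts: suspicious, removed, and removed with BCC confirmed. No size or depth item appears in the readable text. Under 8.2.1 the biopsy diagnosis goes into the eCRF and the detailed report stays in source documents. The planned analyses use histology only to decide whether a removed lesion was a BCC.

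**Step 4. Follow individual lesions through the planned outputs.**

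| Lesion | Removed-BCC count | Contribution to change in suspicious count | AE/SAE status of the lesion itself |
|---|---|---|---|
| Existing, enlarges, not removed | 0 | 0 | Size change excluded (8.3.2) |
| Existing, invasive, removed, confirmed | +1 | −1 | Surgery and histology excluded (11.1.2, 11.1.1) |
| Existing, small, removed, confirmed | +1 | −1 | Same |
| New, not removed | 0 | +1 | New BCC excluded (11.1.2) |

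Rows two and three are identical, so the counts cannot distinguish a serious lesion from a trivial one. Under SAP 5.3.1 summaries use observed data only, so a subject who leaves because of progression and has no Month 12 value is absent from the Month 12 change.

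**Step 5. What other routes exist?**

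- The paralesional TEAE row (SAP 6.4.2.1, term undefined) and the lack-of-efficacy factor in causality assessment (Protocol 11.1.5) both need an AE to have been recorded first.
- The death table (SAP 6.4.2.3) draws on the End of Treatment and End of Study pages as well as the AE log, but captures only fatal cases.
- Discontinuation reasons and the aBCCdex lesion score do not identify a serious lesion.
- A consequence such as functional loss is not expressly exempt. However, 11.1.2 asks for each event to be recorded as a single diagnosis where possible, and a site may decide that the diagnosis is BCC, which is exempt.

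**The case against.** The strongest case for the present text has four parts.

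1. **Routine BCCs are expected and recur in this population.** Keeping them out of AE tables is a defensible choice, and BCC surgeries really are an endpoint. This stands: the exemption is sound for ordinary lesions.
2. **The exemptions concern lesions, counts, size, histology and surgery, not outcomes.** Protocol 11.1.3 keeps disability and medically important events as SAEs. Its standard-of-care hospitalization exception would be largely needless if everything BCC-related were already barred. Section 8.3.2 still makes clinically significant examination changes AEs. This also stands, and it means a reader would go too far in inferring that serious harm cannot appear in the safety data. What remains is ambiguity about which rule governs.
3. **Subjects are not simply left untreated.** A reader might infer from "The subject is willing to forego treatment of facial BCCs with anything other than the study IP" that surgery is deferred and that lesion growth is thus a risk imposed by the study. The same criterion makes an exception where the Investigator believes delay might compromise health. Section 7.2 allows removal at any time after Baseline at the Investigator's discretion, and 8.2 schedules recommended and consented Baseline lesions for removal before the next quarterly visit. These texts need reconciling, but they do not show a harm of deferral. Nor does Section 6: together with 6.2, it attributes loss of eyelid, nose or ear function to surgery, not to untreated lesions.
4. **Lesion detail is not wholly uncollected.** Biopsy of removed lesions is mandatory and the diagnosis is in the eCRF. Section 8.2.3 and some Table 1 rows are also not readable in the public text. The supportable statement is that no size item is visible and that histology beyond BCC yes/no has no planned analysis.

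A further fair point is that the medically important criterion includes events that may need surgical intervention. An unqualified seriousness exception could therefore sweep in many routine removals, and any fix must prevent that.

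**Conclusion.** The point holds as a gap in the reporting rule. The exemption in 11.1.2 covers SAEs and has no seriousness limit, 8.3.2 excludes size change without limit, and two of the three endpoints cited as grounds are absent from all 14 listed endpoints. Serious progression of a facial BCC may therefore not be visible in the TEAE and SAE tables or trigger 24-hour notification, and it enters the efficacy counts as at most one lesion.

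The number of events affected cannot be estimated, because the documents give no rate for serious facial BCC outcomes. It would be tempting to turn a zero count among the maximum of about 200 subjects into an upper limit on the rate. That would say nothing about how many events the rule keeps out, since sites may or may not report consequences under it.

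The conclusion assumes that the unreadable parts of Table 1 and Section 8.2.3 contain no lesion size or severity item, and that sites follow the exemption as written.

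**What to change.** Protocol amendment:

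- In 11.1.1, 11.1.2 and 8.3.2, state that the exemption does not apply when a facial BCC or its consequence meets a seriousness criterion in 11.1.3. Such events are reported as SAEs under 11.1.6.
- Keep the existing standard-of-care hospitalization exception, and state that routine removal of a BCC does not by itself meet the medically important criterion.
- Delete new BCCs and nSEBs from the endpoint examples in 11.1.2.
- Reconcile inclusion criterion 11 with 7.2 and 8.2 on when facial BCCs are treated. Which text should govern is for the sponsor to decide.

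SAP:

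- Add one row to the overall AE summary in 6.4.2.1 for facial BCC events meeting a seriousness criterion.
- Tabulate the biopsy diagnoses already captured in the eCRF.

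The cost is a short amendment, one table row and one table from existing data, with no new assessment. The downside is that some disease-related SAEs will be reported that are not reported now. The documents do not allow their number to be predicted.
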